- **Olaratumab Monotherapy Treatment Period:** begins at the first administration of olaratumab 20 mg/kg on Day 1 of Cycle 1 and ends on Day 21 of Cycle 1.
- **Combination Olaratumab plus Doxorubicin Therapy Treatment Period:** begins after the post Cycle 1 treatment biopsy is obtained, with the first administration of olaratumab 20 mg/kg and doxorubicin 75 mg/m² on Day 1 of Cycle 2, followed by the administration of olaratumab 20 mg/kg on Day 8 of Cycle 2. This treatment period continues from Cycle 3 through Cycle 7 with the administration of olaratumab at a dose of 15 mg/kg on Days 1 and 8 and doxorubicin 75 mg/m² on Day 1 of each 21-day cycle. Upon completion of the combination therapy treatment period, the patient will no longer receive study treatment.
- **Post-discontinuation Follow-Up:** begins the day after the patient and the investigator agree that the patient will no longer continue study treatment.
 - **Short-term follow-up:** begins the day after the patient and the investigator agree that the patient will no longer continue study treatment and lasts approximately 30 days (±7 days). The short-term follow-up visit occurs at or near the end of the short-term follow-up period (±7 days).
 - Follow-up for safety - Patients who undergo surgical resection will be followed for safety for approximately 30 days (±7 days) after surgery.
 - **Long-term follow-up:** begins the day after short-term follow-up is completed.
 - Follow-up for progression - Patients who discontinue study treatment, or have completed 6 cycles of combination therapy, and have not progressed and have not initiated a new systemic treatment for their disease will be assessed for progression by imaging studies every 6 weeks (<7 days) until PD. Patients who have had surgical resection will not be followed for subsequent progression by imaging studies.

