10.6. Efficacy

The following secondary efficacy endpoints will be measured:

Progression-free survival (PFS): is defined as the time from enrollment until the first radiographic documentation of objective progression as defined by RECIST (v1.1) ([Attachment 8](#)), or death from any cause. Patients who die without a reported prior progression will be considered to have progressed on the day of their death. Patients who did not progress or who are lost to follow-up will be censored at the day of their last radiographic tumor assessment. If no baseline or postbaseline radiologic assessment is available, the patient will be censored at the date of enrollment. If death or PD occurs after 2 or more consecutive missing radiographic visits, censoring will occur at the date of the last radiographic visit prior to the missed visits. The use of a new anticancer therapy or the performance of a surgical resection prior to the occurrence of PD will result in censoring at the date of last radiographic assessment prior to initiation of new therapy or surgical resection.

3-month PFS: estimated as the total number of patients who did not progress 3 months after enrollment divided by the total number of patients.

Overall response rate (ORR): estimated as the total number of CRs, complete responses unconfirmed (CRus), and PRs divided by the total number of patients.

Disease control rate (DCR): is computed as the total number of patients with the best overall response of CR, CRu, PR, or SD divided by the total number of patients.

Rate of Resectability: is defined as the total number of patients who are resectable (see definition of resectability in Section 4) divided by the total number of patients.

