Efficacy Assessments	Attachment 8	Imaging Studies (CT/MRI) Tumor Assessments (according to RECIST v1.1)	X (if applicable)	X	For patients who discontinue study treatment, or complete 6 cycles of combination therapy, and have not progressed, imaging studies and tumor assessments are to be obtained every 6 weeks (±7 days) until PD, irrespective of treatment cycles, until documented progression as calculated from baseline scan. Patients who have had surgical resection will not be followed for subsequent progression by imaging studies. CT/MRI scans will be read locally and a scan will also be sent for storage at a central vendor.

Procedure Category	Protocol Section	Procedure	Study Period		Comments
			Posttreatment Discontinuation Follow-Up		
			Short-Term Follow-Up	Long-Term Follow-Up	
			Visit	801	
Duration	30 ± 7 days		See footnote for duration		
Adverse Events Collection/CTCAE Grading	8.1.2	Toxicity assessment	X	X ^a	All AEs considered at least possibly related to study treatment will be followed until resolution, stabilization, or return to baseline, or until deemed irreversible. After the 30-day short-term follow-up visit, only new and ongoing SAEs deemed related to study treatment will be collected.
Concomitant Medication Notation	7.5	Concomitant medications	X		
Patient Disposition			X	X	At the time that the patient is discontinued from study participation, information regarding the patient status will be collected.

Abbreviations: AE = adverse event; CT = computed tomography; CTCAE = Common Terminology Criteria for Adverse Events; ECG = electrocardiogram; ECOG = Eastern Cooperative Oncology Group; eCRF = electronic case report form; IRR = infusion-related reaction; MRI = magnetic resonance imaging; MUGA = multi-gated acquisition; PD = progressive disease; PK = pharmacokinetic; RECIST = Response Evaluation Criteria in Solid Tumors; SAE = serious adverse event; UA = urinalysis.

Short-term follow-up begins the day after the patient and the investigator agree that the patient will no longer continue study treatment and lasts approximately 30 days (±7 days).

The short-term follow-up visit occurs at or near the end of the short-term follow-up period (±7 days).

^a Follow up for safety: Patients who undergo surgical resection will be followed for safety for approximately 30 days (±7 days) after surgery.

Long-term follow-up begins the day after short-term follow up is completed.

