Progressive Disease (PD): At least a 20% increase in the sum of the diameters of target lesions, taking as reference the smallest sum on study (including the baseline sum if that is the smallest). In addition to the relative increase of 20%, the sum must also demonstrate an absolute increase of at least 5 mm. The appearance of one or more new lesions is also considered progression.

For equivocal findings of progression (for example, very small and uncertain new lesions; cystic changes or necrosis in existing lesions), treatment may continue until the next scheduled assessment. If at the next scheduled assessment, progression is confirmed, the date of progression should be the earlier date when progression was suspected.

Stable Disease (SD): Neither sufficient shrinkage to qualify for PR nor sufficient increase to qualify for PD, taking as reference the smallest sum diameters while on study.

Not Evaluable: When an incomplete radiologic assessment of target lesions is performed or there is a change in the method of measurement from baseline that impacts the ability to make a reliable evaluation of response.

Evaluation of Nontarget Lesions

Complete Response: Disappearance of all nontarget lesions and normalization of tumor marker level. All lymph nodes must be non-pathological or normal in size (<10mm short axis).

Non-CR/ non-PD: Persistence of 1 or more nontarget lesions and/or maintenance of tumor marker level above the normal limits.

Progressive Disease: Unequivocal progression of existing nontarget lesions. The appearance of 1 or more new lesions is also considered progression.

Not Evaluable: When a change in method of measurement from baseline occurs and impacts the ability to make a reliable evaluation of response.

Evaluation of Best Overall Response

The best overall response is the best response recorded from the start of the study treatment until the earliest of objective progression or start of new anticancer therapy, taking into account any requirement for confirmation. The patient's best overall response assignment will depend on the findings of both target and nontarget disease and will also take into consideration the appearance of new lesions. The Best Overall Response will be calculated via an algorithm using the assessment responses provided by the investigator over the course of the trial.

Time Point Response

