- **Consolidated AEs** are composite AE terms consisting of synonymous Medical Dictionary for Regulatory Activities (MedDRA) preferred terms (PTs) to allow meaningful interpretation of the AE data. Consolidated AE categories and PTs will be maintained at compound level and reported in the CSR.
- **Serious adverse event (SAE)** is any AE that results in one of the following outcomes:

- death
 - a life-threatening experience (that is, immediate risk of dying)
 - persistent or significant disability/incapacity
 - initial or prolonged in-patient hospitalization
 - congenital anomaly/birth defect
 - considered significant by the investigator for any other reason
- **Treatment-emergent adverse event (TEAE)** is defined as an event that first occurred or worsened in severity after baseline and 30 days after the last dose of study treatment and related SAEs reported beyond 30 days after the last dose of study treatment, where last dose stands for actual dose, that is, 0 dose is not counted as last dose.

Exposure-related variables are listed below:

- **Dose exposures:** As reported in the eCRF
- **Number of dose level reductions:** Sum of the number of dose level reductions as reported in the eCRF
- **Dose delays:** As reported in the eCRF
- **Dose withheld/skip (Not Administered):** As reported in the eCRF
- **Dose interruption:** As reported in the eCRF

5.3.5. *Efficacy Variables*

The study was not designed to make an efficacy assessment. However, any tumor response data will be tabulated according to assigned treatment.

Circulating tumor cells (CTC) will be assessed at pre-olaratumab and post-olaratumab in whole blood.

Secondary efficacy analysis will be performed to investigate antitumor activity by assigned treatment. Response and disease progression will be evaluated using Response Evaluation Criteria in Solid Tumors (RECIST) version 1.1 (Eisenhauer et al. 2009) for all tumors.

Overall Response Rate (ORR) is defined as the percentage of patients achieving a best overall response of either Complete Response (CR), complete responses unconfirmed (CRus) or Partial Response (PR), as determined by RECIST 1.1. The best overall response is the best response from the start of the treatment until PD/recurrence.

Disease control rate (DCR) is defined as the percentage of patients achieving a best overall response of CR, CRu, PR, or SD as determined by RECIST 1.1. Patients who do not have any

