postbaseline tumor response assessments for any reason are considered non-responders and are included in the denominator when calculating the response rate.

Progression-free survival (PFS) is defined as the time from the date of first study dose to the first date of radiologic disease progression or death due to any cause. [Table JGDM.5.1](#) defines the rules of censoring to be applied to PFS.

3-month Progression-free survival (PFS) is defined as the 3-month PFS rate as estimated using Kaplan-Meier methods. PFS is as defined above.

Rate of Resection is defined to be the percentage of patients whose tumors are determined to be resectable divided by the total number of patients. The evaluation of resectability of a tumor is determined by the surgeon in consultation with the multi-disciplinary team, and depends on the tumor stage and the patient's co-morbidity. The primary aim of surgery is to completely excise the tumor with a margin of normal tissue.

Table JGDM.5.1. Censoring Rule of PFS Primary Analysis

Situation	Event / Censor ^d	Date of Event or Censor ^e
Tumor progression^a or death	Event	Earliest date of PD or death
No tumor progression and no death	Censored	Date of last adequate radiological assessment or date of first study dose
unless		
No baseline radiological tumor assessment available	Censored	Date of first study dose
No adequate^b postbaseline radiological tumor assessment available and death reported after 2 scan intervals ^c following first study dose	Censored	Date of first study dose
New anticancer treatment (including surgery) started and no tumor progression or death within 14 days	Censored	Date of adequate radiological assessment prior to (start of new therapy +14 days) or date of first study dose (whichever is later)
Tumor progression or death documented immediately after 2 or more consecutive missing scan intervals following last adequate radiological tumor assessment or first study dose (whichever is later)	Censored	Date of last adequate radiological assessment prior to the missing assessment or date of first study dose

Abbreviations: CR = complete response; PD = progressive disease; PFS = progression free survival; PR = partial response; SD = stable disease.

- a Symptomatic deteriorations (that is, symptomatic progressions, which are not radiologically confirmed) will not be considered as disease progressions.

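### SAP Section 5.3.5 lets best overall response run past the start of new anticancer therapy, where protocol Attachment 8 stops it

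*SAP*

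**What the plan says.** **Response window, SAP.** Section 5.3.5 states: "The best overall response is the best response from the start of the treatment until PD/recurrence". ORR and DCR are both built on this best overall response.

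**Response window, protocol.** Attachment 8 defines it as the best response "recorded from the start of the study treatment until the earliest of objective progression or start of new anticancer therapy", and says it will be computed by an algorithm from the investigator's assessments. Protocol Section 8.3 sends response evaluation to Attachment 8.

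**New therapy and surgery in PFS.** Both documents deal with these events for PFS only. SAP Table JGDM.5.1 has a censoring row headed "New anticancer treatment (including surgery) started". Protocol Section 10.6 says: "The use of a new anticancer therapy or the performance of a surgical resection prior to the occurrence of PD will result in censoring".

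**Imaging after study treatment.** In protocol Section 6.2, the long-term follow-up definition covers patients who "have not progressed and have not initiated a new systemic treatment for their disease will be assessed for progression by imaging studies". The post-treatment schedule in Attachment 1 covers patients who stop or complete treatment "and have not progressed, imaging studies and tumor assessments are to be obtained every 6 weeks" until PD, with no condition about new therapy. The on-treatment imaging row of Attachment 1 and SAP Section 5.1 also carry on until progression without that condition.

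**The concern.** Best overall response is a maximum over a window, so the end of the window decides which scans can count. A programmer working from the SAP would code the wider window and admit any scan before progression, including one taken while the patient is on a different drug. The resulting ORR and DCR would mix the effect of study treatment with that of whatever followed.

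It would also make the efficacy tables inconsistent with each other. A patient could be censored for PFS when new therapy starts and later become a responder for ORR on the strength of that therapy.

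**Working it through.** **1. The two windows side by side**

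| | Starts | Ends |
|---|---|---|
| SAP 5.3.5 | start of treatment | PD/recurrence |
| Protocol Attachment 8 | start of study treatment | earlier of objective progression or new anticancer therapy |

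They differ for any patient who starts new anticancer therapy before progression and is scanned afterwards.

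**2. Does the SAP restore the cut-off elsewhere?** Section 5.3.5 adds only that patients without a postbaseline assessment are non-responders and stay in the denominator. Section 5.10 gives the ORR and DCR tabulation and a Kaplan-Meier duration of response, with no rule on new therapy. Table JGDM.5.1 has such a rule, but it is a PFS censoring table. So no.

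**3. Can a scan after new therapy exist?** The limit in Section 6.2 removes long-term scans after new systemic treatment. It does not mention non-systemic treatment such as radiotherapy. Attachment 1 and SAP Section 5.1 do not repeat the limit. Exposure is therefore reduced but not removed.

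**4. Which patients would change?** Take a patient without progression when new therapy starts. *None qualifying* means no assessment, or stable disease short of the six-week minimum in Attachment 8.

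| Best response before new therapy | First seen after it, before PD | ORR | DCR |
|---|---|---|---|
| CR or PR | any | unchanged | unchanged |
| SD | CR or PR | +1 patient | unchanged |
| none qualifying | SD | unchanged | +1 patient |
| none qualifying | CR or PR | +1 patient | +1 patient |

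Shortening the window can only leave ORR and DCR the same or lower them, so the SAP wording can only inflate.

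**5. Size.** The documents give no planning figure for ORR or DCR. Their one precision figure is the 95% CI of 31% to 66% for a PDGFRα hit rate of 17/35. The exact (Clopper-Pearson) formula is

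- lower = Beta⁻¹(0.025; x, n − x + 1)
- upper = Beta⁻¹(0.975; x + 1, n − x)

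With x = 17 and n = 35 it gives 31.4% to 66.0%, which reproduces the stated interval. SAP Section 5.10 also asks for exact intervals for ORR and DCR, so the same formula applies.

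Weight of one patient: 1/35 = 0.0286, or 2.9 points. The target of 35 is for evaluable patients and replacement is allowed, so the ITT denominator could be larger. If it were 40 (an assumption), the weight would be 1/40 = 2.5 points.

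As an illustration, take the ORR of 18.2% that protocol Section 5.1 reports for the combination in Study JGDG: 0.182 × 35 = 6.4, so about 6 responders. Using it here is an assumption.

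| Responders | ORR | Exact 95% CI |
|---|---|---|
| 6/35 | 17.1% | 6.6% to 33.6% |
| 7/35 (one misattributed) | 20.0% | 8.4% to 36.9% |
| 8/35 (two misattributed) | 22.9% | 10.4% to 40.1% |

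**The case against.** **The protocol already has the right rule.** Section 8.3 points to Attachment 8, and the SAP sentence may be no more than a loose paraphrase. That is a fair account of how it arose. But the SAP sentence is explicit, and its general reference to RECIST 1.1 does not override it.

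**Little later therapy can enter.** Protocol Sections 7.5 and 7.5.2 bar other anticancer therapy on study treatment. Section 6.3.2 requires study drug to stop before another effective agent is introduced. Section 8.1.2.2.3 asks for the follow-up assessments to be completed first if new therapy starts early. An explicit limit in Section 6.2 also outweighs silence in a schedule comment. All of this stands as a reason to expect few cases. It does not close the gap, because Attachment 1 is what sites follow for scan timing, and non-systemic therapy is outside the limit.

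**Surgery.** A reader might infer that a scan after excision could be read as a complete response, and that the 14-day allowance in Table JGDM.5.1 invites such scans. The documents do not support this. Section 6.2 says: "Patients who have had surgical resection will not be followed for subsequent progression by imaging studies", Attachment 1 repeats it, and SAP Section 5.1 leaves resected patients out of six-weekly follow-up. The 14-day allowance fixes a PFS censoring date and schedules no scan. Attachment 8 does not name surgery, so the conflict with the protocol concerns new therapy alone.

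**Importance.** SAP Section 5.3.5 itself says the study was not designed to assess efficacy. ORR and DCR carry no hypothesis or decision threshold. This stands and sets the weight of the point.

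**Conclusion.** Wrong as written, and minor. The SAP's response window contradicts Attachment 8 by omitting the stop at new anticancer therapy, and the error can only raise ORR and DCR. Each affected patient is worth 2.9 points at 35 patients. For DCR, only patients with no qualifying response before the switch matter.

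The conclusion about wording needs no assumption. The conclusion about effect assumes that at least one patient without progression is scanned after starting other therapy. The documents do not say how many would be, and the limit in Section 6.2 suggests few. The primary biomarker objectives and the sample size are untouched.

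**What to change.** In SAP Section 5.3.5, define best overall response as the best response from the start of study treatment "until the earliest of objective progression or start of new anticancer therapy" (including surgery, as classed in Table JGDM.5.1). State that the same window applies to DCR and to duration of response.

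Three notes on the wording:

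- The new-therapy stop restores Attachment 8. The surgery clause does not come from there. It is added for consistency with Table JGDM.5.1 and protocol Section 10.6, and has little practical effect because resected patients have no scheduled progression scans.
- Extending the window to duration of response is also an addition, since Attachment 8 runs that duration to recurrence or progression. Section 5.10 should state the censoring date.
- The response window will still not match SAP PFS exactly, because Table JGDM.5.1 accepts assessments up to 14 days after new therapy starts. The SAP should not claim that it does.

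The cost is one clause in Section 5.3.5 and a line in Section 5.10. No patients, visits or data are added, and the sample size does not change.

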- b Adequate radiological tumor assessment refers to an assessment with one of the following responses: CR, PR, SD, or PD.
- c The 2-scan interval is counted from the date of last adequate tumor assessment to the date of next 2 scheduled tumor assessments plus 14 days (adjusted by tumor assessment window).
- d Refer to flow chart in [Appendix 1](#) if a patient meets multiple censoring criteria.
- e If there are multiple dates associated with 1 assessment, the assessment date will be set to the first date when the overall response is PD and the last date otherwise.

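### The SAP's definition of an adequate scan omits non-CR/non-PD, so some patients with nonmeasurable disease only would be censored for PFS at first dose

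*SAP*

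**What the plan says.** **Who can enter and how their scans are coded.** Inclusion criterion 5 (Protocol 6.1.1) accepts measurable disease, or nonmeasurable disease that can be evaluated. For patients with nontarget lesions only, Protocol Attachment 8, Table 2, gives persistent disease without progression the overall response non-CR/non-PD. Its footnote prefers that label to SD.

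**SAP rule.** Footnote b to Table JGDM.5.1 (SAP 5.3.5) reads: "Adequate radiological tumor assessment refers to an assessment with one of the following responses: CR, PR, SD, or PD". The table uses this definition in several rows:
- No progression and no death: censored at "Date of last adequate radiological assessment or date of first study dose".
- No adequate postbaseline scan, and "death reported after 2 scan intervals" following first dose: censored at first dose.
- New anticancer treatment, including surgery: censored at an adequate assessment before the start of that treatment plus 14 days, or at first dose.

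**Protocol rule.** Protocol 10.6 sets no adequacy condition. "Patients who did not progress or who are lost to follow-up will be censored at the day of their last radiographic tumor assessment". "Patients who die without a reported prior progression will be considered to have progressed on the day of their death", except after two or more consecutive missed radiographic visits. For surgery, "performance of a surgical resection prior to the occurrence of PD will result in censoring at the date of last radiographic assessment" before the resection. Censoring at time zero is reserved for patients with no baseline or no postbaseline assessment.

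**The concern.** The protocol defines a response category, and the SAP's censoring table has no place for it. A nonmeasurable-only patient can be scanned on schedule, show no progression each time, and still have no adequate postbaseline assessment. The SAP then discards progression-free time that the protocol keeps, and turns a late death that the protocol counts into a censored observation. PD at one of the first two scans, or death within 2 scan intervals, still counts as an event. Only the favorable follow-up is lost, which pulls the 3-month PFS estimate down.

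Resection matters here because the population is potentially resectable. Protocol 6.2 says: "Patients who have had surgical resection will not be followed for subsequent progression by imaging studies". For a resected patient, no later scan can move the censoring date away from first dose.

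**Working it through.** No sample size or other stated figure depends on this rule, so there is nothing in the plan to reproduce. The check has two parts.

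**1. The rules applied to example patients.**
- Scans are every 6 weeks (Protocol Attachment 1), so days 42, 84 and 126.
- Footnote c to Table JGDM.5.1 makes 2 scan intervals 2 × 42 + 14 = 98 days.
- Cycle 7 ends on day 7 × 21 = 147.
- The few days between enrollment and first dose are ignored. N/N stands for non-CR/non-PD.

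| Patient | SAP as written | Protocol 10.6, literally | SAP with N/N added to footnote b |
|---|---|---|---|
| N/N on days 42, 84, 126; alive | censored at first dose | censored day 126 | censored day 126 |
| Same scans, resected after day 147 | censored at first dose | censored day 126 | censored day 126 |
| Same scans, death on day 150 | censored at first dose | event day 150 | event day 150 |
| N/N on day 42, death on day 70 | event day 70 | event day 70 | event day 70 |
| N/N on day 42, NE on day 84; alive | censored at first dose | censored day 84 | censored day 42 |
| NE on days 42 and 84 only; alive | censored at first dose | censored day 84 | censored at first dose |

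The first three rows are the defect. The fourth shows that an early death is unaffected. The last two show that NE is a separate matter, which the added term does not settle.

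**2. Size for 3-month PFS.** The SAP estimates this by Kaplan-Meier. Inputs: N = 35 (both documents); k affected patients (assumed, 0 to 3); p, the true 3-month PFS, the same for everyone (assumed, 40% to 80%). I also assume that no affected patient who is progression-free at 3 months has PD recorded later, and that there is no other censoring before 3 months. On average kp patients then leave the risk set at first dose without an event, while all 35(1 − p) events remain:

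estimate = (35p − kp) / (35 − kp)

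- k = 0: no change.
- k = 1, p = 0.4: 13.6/34.6 = 39.3%, a fall of 0.7 points.
- k = 1, p = 0.8: 27.2/34.2 = 79.5%, a fall of 0.5 points.
- k = 3, p = 0.4: 12.8/33.8 = 37.9%, a fall of 2.1 points.
- k = 3, p = 0.5: 16/33.5 = 47.8%, a fall of 2.2 points.
- k = 3, p = 0.8: 25.6/32.6 = 78.5%, a fall of 1.5 points.

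These figures average over whether the affected patients progress. If one affected patient is in fact progression-free, and 14 of 35 have an event by 3 months, 21/35 = 60.0% becomes 20/34 = 58.8%.

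For comparison, the 95% half-width at 60% is 1.96 × √(0.6 × 0.4/35) = 16.2 points.

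**DCR, separately.** Each non-progressing patient left out of the numerator is worth 1/35 = 2.9 points; three are worth 3/35 = 8.6 points.

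**The case against.** **There may be no such patients.** Inclusion criterion 1 requires a primary lesion that can be biopsied repeatedly, and such a lesion will often be measurable. Inclusion criterion 5 also lets an irradiated lesion be a target lesion after a confirmatory biopsy at least 90 days after radiotherapy, although Attachment 8 gives only the progression exception. This stands, and it is a main reason for the low rating.

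**Sites may record SD.** The Attachment 8 footnote states a preference and does not forbid SD. A scan recorded as SD or CR is adequate, and that patient is not affected. The SAP nowhere maps non-CR/non-PD to SD, so the gap remains whenever the preferred code is used.

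**Later PD.** A reader might infer that PD at the third scan would restore the patient as an event, or equally that it would certainly be lost. The documents settle neither. Table JGDM.5.1 censors PD found immediately after two or more missing scan intervals, and footnote c counts from the last adequate assessment. If non-CR/non-PD scans count as missing, PD on day 126 lies beyond 98 days and is censored at first dose. If missing means not performed, it is an event. In the first case the 0.5 to 2.2 points apply whether or not PD follows at a later scheduled scan. In the second, the fall is smaller to the extent that PD is recorded later.

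**NE scans.** A reader might extend the point to patients with NE scans only. Their first-dose censoring comes from the exclusion of NE, not from this omission.

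**DCR.** A reader might see a second contradiction here, but Protocol 10.6 and SAP 5.3.5 and 5.10 agree on the DCR categories. Whether these patients fall outside DCR depends on a best-overall-response algorithm that Attachment 8 mentions but does not set out.

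**Flow chart.** SAP Appendix 1 governs patients who meet several censoring criteria. Its figure is missing from the available text and could not be checked.

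**Conclusion.** The point holds in a narrow form. For a patient whose evaluable postbaseline scans are all recorded as non-CR/non-PD, with no PD and no death within about 98 days of first dose, Table JGDM.5.1 read literally contradicts Protocol 10.6 and censors at first dose.

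The effect is small: about 0.5 to 2.2 points off 3-month PFS for an assumed 1 to 3 such patients in 35, under the assumptions shown, and none if there are no such patients. That is well inside the sampling error. PFS and 3-month PFS are secondary and descriptive, SAP 5.3.5 itself says that the study was not designed to assess efficacy, and the primary biomarker analysis does not use these rules. A reader might infer that the PFS results would be seriously distorted; nothing in the documents supports that. Severity: minor. The literal gap in footnote b is certain; how many patients it touches, and the DCR consequence, are not.

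**What to change.** In SAP Table JGDM.5.1, footnote b, add non-CR/non-PD to the adequate responses, or state that it is treated as SD for PFS. This costs one term in a footnote and needs no new data.

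The change removes the conflict for non-CR/non-PD scans only. It does not bring the SAP fully into line with Protocol 10.6, because three differences remain: the exclusion of NE scans, the time origin (first dose in the SAP, enrollment in the protocol), and the 14-day allowance around new therapy or surgery.

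Secondary, and only if the best-response algorithm does not already map non-CR/non-PD to SD: count non-CR/non-PD in DCR and show it as its own row. Apply the 6-week minimum from first dose that Attachment 8 sets for SD, so that one early scan does not count as disease control. This needs a line in Protocol 10.6, and therefore a protocol change, with matching lines in SAP 5.3.5 and 5.10. DCR would then include a category without tumor measurement, which is why it should be shown separately.
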